14.1 Randomization

Randomization Type

Not applicable.

Unblinding and Derandomization

Not applicable.

14.2 Sample Size Determination

As this is an exploratory study, no sample size calculation was performed. The sample size was chosen based on the experience of proDERM with this type of study.

14.3 Analysis Population

For this study the following analysis populations will be defined:

Screening Population: Includes all subjects who provided at least written informed consent and reason for termination are documented.

Safety Population (SP): Includes all subjects who were enrolled into the study. Safety will be done on all available data for safety population.

Per Protocol (PP) population: Includes all subjects randomized in the study in accordance with both the in- and exclusion criteria who finished the study according to protocol without major protocol violations and who will not have withdrawn their consent.

Major violations may be for example:

inclusion / non-inclusion criteria not respected,

interfering therapy,

poor compliance to study treatment administration or protocol requirements,

unblinding.

All protocol violations are judged by the Investigator whether deviations are regarded as minor or major and thereby whether a subject has to be excluded from PP population.

14.4 Analysis of Data

The statistical analysis is specified in detail in the statistical analysis plan (SAP). If the content of the SAP deviates from the proceeding as described in the protocol, this is documented in the SAP, together with reasons and consequences. For this study the following analysis will be defined:

Missing Data

No replacement of missing data will be performed and the affected assessments will be regarded as lost for analysis.

Demographic Data

Demographic variables (age, gender, smoker or non-smoker, type of normally consumed tobacco or, e-cigarette) will be given for each defined analysis population. Data will be summarized using frequency distributions (number and percentage) for categorical/ordinal variables and mean, standard deviation and range for continuous variables.

Data Listing

Medical history (concomitant diagnoses and therapies) and reasons for termination will be listed for all subjects in the screening population.

Safety and tolerability data (AEs, concomitant medication) will be listed for the Safety Population.

The assessment time at t0 (before product use) will be defined as Baseline.

Sensory evaluation of oral odour (intensity scoring and hedonic scale):

- Raw Data will be listed by treatment, assessment time and odour judge for all subjects in PP population.
- Mean scores over all graders will be given per subject, treatment and assessment time.
- Differences to Baseline will be calculated per subject, treatment and assessment time on mean scores.

Measurement of exhaled carbon-monoxide levels will not be listed but reordered in an excel document.

Descriptive Data Analysis

Sensory evaluation of oral odour (intensity scoring and hedonic scale):

- N, mean, standard deviation, median, minimum, maximum and 95% confidence limits will be given for calculated values by treatment and assessment time for each parameter.
- The mean values of calculated values (e.g. mean values and differences to baseline) over subjects will be presented in bar charts by treatment and assessment time with 95% confidence intervals for each parameter.

Statistical Data Analysis

The statistical analysis for the sensory evaluations is based on the PP Population only. Due to the explorative character of the study, no adjustment for multiplicity will be done.

Primary Hypotheses

Comparison of treatment A and B will be performed on differences to Baseline values for each parameter separately by a one-sided t-Test for independent samples with a significance level of 0.025 (alpha).

The following hypothesis will be tested for the intensity scoring:

 H_0 : $\mu_A \ge \mu_B$ H_1 : $\mu_A < \mu_B$

The following hypothesis will be tested for the hedonic scale:

 $H_0: \mu_A \le \mu_B$ $H_1: \mu_A > \mu_B$

Where μA denotes the mean difference to Baseline for treatment A and μB denotes the mean difference to Baseline for treatment B.

Secondary Hypotheses

A significance level of 0.05 (alpha) is chosen for the secondary analysis.

- Comparisons of treatments (A vs. C, B vs. C) will be performed on differences to Baseline values for each parameter separately by a t-Test for independent samples.
- Comparisons of assessment times will be performed on mean scores for each treatment and parameter separately by a paired t-Test.

The computation of the statistical data will be carried out with a commercially available statistics program (SAS for Windows).

15 Deviations / Protocol Modifications

Any deviation from this Protocol will be discussed with the Sponsor and appropriately documented. The Investigator is responsible for any deviation from the protocol and documentation of this deviation in the study records and the final report.

If it becomes necessary to make a change to the approved Protocol (i.e. signed), the Investigator and the Sponsor will agree to the change before it is implemented. The change and the reason for it will be documented in an amendment. If a change is necessary on an emergency basis, the Sponsor will be notified as soon as possible after the action has been taken.

16 Final Report

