3.2 Selection of Subjects

All below mentioned inclusion, exclusion criteria and instructions for the subjects will be checked by a questionnaire before the start of the study and during the study. Conditions developing during the course of the study listed in the exclusion criteria and instructions as well as protocol deviations do not necessarily lead to the subject's exclusion. The investigator decides whether the subject is still eligible.

The subjects will be instructed to inform the study site in case of medical problems or changes in therapies.

Inclusion Criteria

- Written Informed Consent to participate in the study
- · Willingness to actively participate in the study and to come to the scheduled visits
- Subjects must demonstrate the ability to comprehend the Informed Consent Form (ICF), be able to communicate well with the Investigator or their appropriately qualified designee, understand and comply with the requirements of the study, and be judged suitable for the study in the opinion of the Investigator or their appropriately qualified designee
- · Female or male
- 21 to 60 years of age
- Average oral hygiene (tooth brushing at least twice a day)
- Good general health as judged by the Investigator or their appropriately qualified designee based on their medical history
- 1/3 of the panel: regular cigarette smoker (manufactured filter cigarettes, excluding menthol cigarettes; have smoked for at least 3 consecutive years prior to screening; typically smoke at least 10 cigarettes per day) with CO-level >7 ppm at Screening
- 1/3 of the panel: regular e-cigarette consumer r, willing to use a test e-cigarette (uses a minimum of 160 puffs per day for more than 6 months prior to screening, uses only e-cigarettes) with CO-level ≤6 ppm at Screening
- 1/3 non-smokers (have never smoked (<100 cigarettes in their life and none within 1 year prior to screening) and willing to continue not to smoke or use any form of tobacco for the duration of the study (exhaled CO level ≤ 6ppm).

Exclusion Criteria

- Female subjects: Pregnancy or lactation
- · Drug addicts, alcoholics
- AIDS, HIV-positive or infectious hepatitis if known to the subjects
- Conditions which exclude a participation or might influence the test reaction/evaluation
- Participation or being in the waiting period after participation in similar cosmetic and/or pharmaceutical studies
- Any pathological change of the oral mucosa or gingival (e.g. allergic reactions, ulceration candidiasis)

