5.1 Description of Test Procedure

Screening:

The subjects will come to the Study Site. They will be informed about the study by a dentist and give their written consent. Medical history and concomitant therapies will be documented. A dentist will perform an oral and dental examination. The eligibility of each subject will be evaluated according to the inclusion/exclusion criteria by a dentist. Exhaled CO-levels will be measured. Subjects fulfilling the inclusion/exclusion criteria will be enrolled into the study. Images of the normally used brand of cigarettes or e-cigarettes/e-liquid will be taken for documentation purposes and the brand will be documented.

Day 1:

The subjects will return to the study site.

Exhaled CO-levels will be measured; subjects who do not match the criteria will be excluded. Subject will brush their teeth for 2 minutes using the supplied toothpaste and toothbrush.

First baseline (t0) organoleptic scores will be assessed 2 hours \pm 15 minutes after brushing by 6 experienced and trained odour judges. Then, the smoking subjects will use the test product at the study site (outside of the test institute building) according to Sponsor's product instructions and under supervision of a technician. Non-smokers will have a waiting period. Smoking and e-cigarette subjects will return to the study room and 5 minutes \pm 2 min after use of product, the organoleptic assessments will be started for all subjects.

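### All sensory tests and score listings are confined to a per-protocol set with discretionary membership, so the effect of exclusions on A versus B cannot be checked

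*Protocol*

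**What the plan says.** Section 14.4 of the Protocol names a single analysis set for intensity and hedonic scores: "The statistical analysis for the sensory evaluations is based on the PP Population only". The listing rule has the same limit: "Raw Data will be listed by treatment, assessment time and odour judge for all subjects in PP population". The contents of the final report (16.1) likewise promise raw data for valid subjects.

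Section 14.3 defines the set: "Includes all subjects randomized in the study in accordance with both the in- and exclusion criteria who finished the study according to protocol", without major violations and without withdrawal of consent. Major violations are given as examples, not as a closed list. The decision is delegated: "All protocol violations are judged by the Investigator whether deviations are regarded as minor or major", and that call settles whether the subject leaves the per-protocol (PP) set.

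On randomisation, 14.1 says "Not applicable". Groups follow existing habit, one third of the panel each (3.2). Section 1.4 calls the study open-label, while 5.3 has the odour judges score blind behind a non-transparent wall.

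Section 3.1 expects about 33 subjects to enter, using the word 'randomized', and 30 to finish. The primary comparison (14.4) is a one-sided independent-samples t-test of A versus B on change from baseline, at 0.025, for each scale.

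**The concern.** The only set used for inference is one whose membership is partly a matter of judgement. There is likely to be something to judge. Section 3.2 sets many odour-related conditions (coffee, garlic, onion, mouthwash, scented products, product use within two hours of the visit), and 5.1 adds timing windows for brushing and assessment. For conditions and deviations arising during the study, 3.2 says "The investigator decides whether the subject is still eligible". A subject can therefore be kept, scored at t0 and t1, and later be classed as a major violator. That subject's scores would enter no test and no listing.

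The Investigator knows each subject's group, and the Protocol does not say that the classification is made without sight of the scores. In groups this small, one or two such decisions can move the estimated A minus B difference. A reader of the report would see the decisions but could not gauge their effect.

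Separately, the definition of the only inferential set rests on an event that 14.1 says does not occur.

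**Working it through.** **Subject numbers.** The Protocol has no sample-size calculation to reproduce (14.2), so only the counts in 3.1 can be used.

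- Per group at entry: 33 / 3 = 11. Per group at the end: 30 / 3 = 10.
- Expected loss: (33 − 30) / 33 = 9.1%, or about one subject per group.
- Weight of one exclusion: 1 / 11 = 9.1% of an arm.

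**Shift in the mean from one selective exclusion.** Assume normal change scores with SD 1 and no true difference. The expected largest of 11 standard normal values is about 1.59. Removing it leaves ten values whose sum has expectation −1.59, so their mean shifts by 1.59 / 10 = 0.16 SD. Doing the same in the opposite direction in the other arm doubles this: 2 × 0.16 = 0.32 SD. The simulated shift was 0.318 SD.

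**Effect on the error rate.** The simulation used 200,000 trials with normal data, equal SD, 11 per arm, no true difference and the pooled one-sided t-test at 0.025. All selective removals favour A.

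| Subjects analysed | Rejection rate |
|---|---|
| All, 11 v 11 | 0.026 |
| Loss unrelated to outcome, 10 v 10 | 0.025 |
| Least favourable subject removed from A, 10 v 11 | 0.061 |
| One removed from each arm, 10 v 10 | 0.133 |
| Two removed from A and one from B, 9 v 10 | 0.217 |

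The last row uses up the whole expected loss of three and places it entirely in A and B. SD, normality and the selection pattern are assumptions; the Protocol gives no figures for them.

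**What the report would show about an excluded subject.**

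| Item | In the report? | Where |
|---|---|---|
| That the subject was not analysed, and why | Yes | 16.1; reasons also in 17 |
| Protocol deviations | Yes | 16.1; documentation in 15 |
| Demographics by population | Yes | 14.4 |
| Odour scores at t0 and t1 | No | 14.4 and 16.1 cover PP or valid subjects |
| A versus B with that subject included | No | 14.4, PP only |

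The gap is the last two rows.

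**The case against.** The other side has a good deal to say, and much of it stands.

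- **A reader might infer that exclusions are hidden.** They are not. Sections 16.1 and 17 require the subjects left out and the reasons to be reported, and raw data remain open to Sponsor inspection (18). Only the excluded scores, and hence the effect of excluding them, are missing from the report.
- **A reader might see a conflict between 3.2 and 5.1.** Section 5.1 says of the Day 1 CO measurement that "subjects who do not match the criteria will be excluded". This is a specific exception to the general discretion in 3.2, so the two are consistent. It also precedes brushing, and baseline scoring comes two hours after that, so it cannot be influenced by scores.
- **A reader might call 'unblinding' an empty violation,** because 14.1 marks unblinding as not applicable. That entry sits with derandomisation and reads as code-breaking. The judges score blind (5.3), so a judge learning a subject's group would be a real violation. The term should stay.
- **A reader might conclude that the PP set is empty.** Since 14.3 uses 'enrolled' for the Safety Population and 3.1 uses 'randomized' for entry, the intent is clear. This is a wording error, though it sits in the definition of the only inferential set.
- **A full set need not be primary.** There is no randomised comparison to preserve, and eligibility defines the groups, so a misclassified user would blur the contrast. Keeping PP as the main set is defensible.
- **The SAP, not shown, may settle timing or add an analysis.** It may. But the word 'only' in 14.4 is a stated restriction, and by 14.4 itself an SAP that departs from the Protocol must document this with reasons.

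**Conclusion.** The point holds in limited form. The Protocol restricts every sensory test and score listing to a set whose membership is partly discretionary, and the report would not let a reader see whether the exclusions mattered. One exclusion is about 9% of an arm. The error rates of about 6% (one selective removal) and 13% (one per arm) are upper illustrations: they assume normal data, 11 per arm and removal of exactly the least favourable subject. Exclusion unrelated to outcome leaves the rate at 2.5%. Nothing in the Protocol shows that the Investigator sees scores before classifying deviations, or that selective exclusion is intended, so it would be wrong to read these figures as the trial's actual error rate.

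The exploratory aim and the single-day treatment limit the seriousness; the small groups and the formal one-sided hypotheses keep it from being trivial. It should be fixed, but it does not invalidate the design.

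**What to change.** 1. In 14.3, add a set of all enrolled subjects with both t0 and t1 scores. In 14.4, repeat the A versus B tests on it as a supportive analysis. PP may remain the main set.
2. In 14.4 and 16.1, list sensory scores for all assessed subjects, flagging those outside PP.
3. Replace 'randomized' by 'enrolled' in the PP definition (14.3) and in 3.1.
4. In 14.3, require deviations to be classified and the PP list fixed without sight of the odour scores.
5. Keep 'unblinding' among the examples of major violations, and state that it means a judge learning a subject's group.

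The cost is some wording, one further run of the same tests and a slightly longer listing. No new data are needed.

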16.1 Contents

The report will include the following:

- Adverse events (if any)
- Serious adverse events (if any)
- · Identification of study personnel
- · Any protocol deviations and/or additional remarks
- Adverse reactions (if any) that cannot be described by employed scoring scales
- Interpretation of data
- Figures illustrating the main results
- · Tables with main results
- List of Subjects enrolled and completing the study, and subjects not analyzed, if any, with reasons. Subject numbers only will be detailed.
- · Complete listing of raw data for all valid subjects
- Listing of calculated values
- · Statistical analysis
- QA statement
- Images of cigarettes- /e-cigarettes-brand will be provided on USB stick and will not be included in the final report

16.2 Corrections or Additions to the Final Report

Corrections or additions to the approved (i.e. signed) version of the final report will be in the form of a discernible second version of the final report or by an amendment. This amendment will clearly identify the part of the final report that is being added to or corrected and will be signed and dated by the person responsible.

17 Quality Assurance

The study will be conducted, the analysis performed and the report prepared approximating the main principles of Good Clinical Practice (GCP), and in accordance with relevant national regulations, and approved protocol(s). The principle requirements of the Declaration of Helsinki will be taken into account to protect the rights, safety and well-being of subjects participating in the study.

If, after a study is underway, it becomes necessary to make changes to the approved protocol(s), the revisions and reasons for changes will be documented. Appropriate corrections, additions, or deletions that are made to the study documentation will be dated, explained (if necessary), and initialed by responsible personnel. Processing of clinical research data and data analysis will involve verification of data integrity and statistical procedures. The final analysis will be done on the basis of the complete data of valid cases, reasons for data exclusion will be given. The final analysis will serve as a basis for the study report.

An independent quality assurance unit will be engaged to audit clinical research studies to identify, evaluate and communicate the state of compliance with applicable protocol(s), and the quality system of proDERM. The audit program approved by management will ensure that audits will be performed at regular intervals. Objective evidence pertaining to the correct conduct of studies, the performance of quality control measures for completeness and accuracy of research data, data

analysis, and reporting of results will be given and reported to management and to the Investigator, as appropriate.

18 Archiving

All raw data pertaining to the study will be available for inspection by the Sponsor for compliance monitoring. In addition, specified scientists designated by the Sponsor may, upon appointment, examine any set of data. The study report, and informed consents of the subjects related to the study will be stored for at least 10 years. All other study related data will be stored for at least 3 years.

Administrative Structure

